14.9 Censoring

- Time to meaningful relief will be censored (if appropriate) at the time of the final assessment of meaningful relief. If the patient discontinues for lack of efficacy before achieving meaningful relief, it will be censored at 24 h.
- Time to perceptible relief will be censored (if appropriate) at 24h or the time of final assessment of spontaneous pain relief (if earlier). If the patient discontinues for lack of efficacy before achieving perceptible relief it will be censored at 24 h.
- Time to resolution of blunt trauma will be censored (if appropriate) at the day of the final visit. If the patient discontinues for lack of efficacy, it will be censored at 7 days.
- Time to first use of rescue medication will be censored (if appropriate) at the last day for which diary records are available.

If a patient takes a disallowed analgesic medication and subsequently provides efficacy assessments, rules will be established on a case-by-case basis, taking into consideration whether the disallowed analgesic medication was taken to treat pain in the injured area and the likely duration of effect of the medication. The rules will be documented before the study is unblinded.

Additional data handling rules will be specified in the minutes of the BRM, if any, to cover issues not anticipated in the above stipulations.

CRMB	Trial Substance:	Esflurbiprofen Hydrogel Patch		-254R-0201 20-005165-14	
	Short Title:	Local symptomatic and short-term treatment of pain in acute strains, sprains or bruises of the extremities following blunt trauma	Sponsor: TEIKOKU SEIYAKU CO LTD.		

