Teikoku Chemical Co. Ltd Clinical Study Protocol : TK-254R-0201

Documentation of use of rescue medication, if needed (diary check).

- \square Record changes in the use of concomitant medication (section 6.5.6).
- \square Record information on AEs (section 8.1).
- \Box Spontaneous pain intensity, pain at rest (PAR) (section 7.5.1)
- \Box Injury site pain-on-movement (POM) (section 7.5.1).
- □ Visit 4: Global efficacy assessments (GEA) by patient and investigator (section 7.5.1).
- \Box Adhesive power of patch (section 7.5.1).
- □ Local tolerability assessment (except V2).

Visit 5 (72h \pm 4 h)

- \Box Apply next dose of study medication.
- □ Count used/unused patches & collect used patches.
- □ Check for last intake of rescue medication no later than 6 hours prior to Visit.
- □ Documentation of use of rescue medication
- \square Record changes in the use of concomitant medication (section 6.5.6).
- \square Record information on AEs (section 8.1).
- □ Spontaneous pain intensity, pain at rest (PAR) (section 7.5.1)
- \Box Injury site pain-on-movement (POM) (section 7.5.1).
- \Box Global efficacy assessments (GEA) by patient and investigator (section 7.5.1).
- Responder rate 1 (number of patients achieving 50% reduction from baseline in the VAS score for POM)
- \Box Adhesive power of patch (section 7.5.1).
- □ Local tolerability assessment.

Visit 6 (96h+4h)

- □ Apply next dose of study medication.
- □ Count used/unused patches and collect used patches.
- \Box Use of rescue medication.
- \square Record changes in the use of concomitant medication (section 6.5.6).
- \square Record information on AEs (section 8.1).
- \Box Spontaneous pain intensity, pain at rest (PAR) (section 7.5.1).
- \Box Injury site pain-on-movement (POM) (section 7.5.1).

- \Box Adhesive power of patch (section 7.5.1).
- □ Local tolerability assessment.
- □ Dispense patient card (section 6.5.7) and diary (section 6.5.8) and instruct patient about appropriate use.
- Dispense three patches to the patient.
- \Box The patient is instructed on the method and time of application of study drug (section 6.5.4).

Visit 7 (Day 8 ± 2 days) - Final visit

Procedures for this visit are also to be completed if the patient terminates the study prematurely.

- \Box Count used/unused patches and collect used patches.
- \square Record changes in the use of concomitant medication (section 6.5.6).
- \Box Record information on AEs (section 8.1).

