- 4 =very poor.
- □ "How do you rate this medication as a treatment for your soft tissue injury/contusion?" It is assessed on the following 5-point Likert scale:

0=excellent

1=very good

2=good

3=fair

4=poor

The global efficacy assessments are evaluated by the Investigator at Visits 4, 5 and 7 as the response to following questions:

• "Considering all the ways this treatment has affected the patient since he/she started in the study, how well is he/she doing?" It is assessed on the following 5-point Likert scale:

0 = very good

1 = good

2 = fair

3 = poor

4 = very poor.

Adhesive power of the patch

The adhesive power of the patch will be measured by a 5 point numerical scale ($0=\geq 90\%$ adhered / $1=\geq 75\%$ to <90% adhered / $2=\geq 50\%$ to <75% adhered / 3=>0% to <50% adhered / 4=completely detached) at every visit except V1.

Assessment of local tolerability of the patch

Local tolerability will be assessed by the Investigator according to the following numerical scale:

Score	Definition	
0	No evidence of irritation	
1	Minimal erythema, barely perceptible	
2	Definite erythema, readily visible, minimal edema or minimal papular response	
3	Erythema and papules	
4	Definite edema	
5	Erythema, edema and papules	
6	Vesicular eruption	
7	Strong reaction spreading beyond test site	

Use of rescue medication

Each use of rescue medication will be recorded in the CRF or in the diary. The Investigator/ the patient will record the date and time, the number of tablets taken and the reason for rescue (blunt trauma pain or other).

Resolution of soft tissue injury/contusion

Resolution of soft tissue injury/contusion is assessed by the Investigator at the final study visit. Time to resolution is the time of last application of study medication because the soft tissue injury/contusion has resolved. This is based on the record of applications of study medication and the assessments of efficacy.

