9.7 Efficacy

9.7.1 Outcomes

Primary Outcome

Change from baseline in pain-on-movement (POM) at injured site in mm measured using a 100 mm Visual Analogue Scale (VAS) to Visit 5 (72 hours after commencement of study treatment)

The analysis of the primary endpoint will be adjusted for baseline values. The baseline adjusted difference between active treatment and placebo at 72 hours should be > 10 mm. Magnitude of reduction in pain will be used to determine 'responder rate'.

Secondary Outcomes

Secondary efficacy variables:

- □ POM at injured site in mm measured using a 100 mm VAS at 12, 24, 48,72, 96 and 168 hours after commencement of study treatment
- □ AUC over time during first 12, 24, 48, 72, 96 and 168 hours for POM measured using a VAS; ordinate = POM score in mm, abscissa = time after treatment
- □ Pain-at-rest (PAR) at injured site in mm measured using a 100 mm VAS at 12, 24, 48 72, 96 and 168 hours

- □ Reduction in VAS for POM from baseline:
- \Box Time to meaningful reduction (30%)
- \Box Time to optimal reduction (50%)
- Time to complete resolution of pain
- □ Responder rate 1 (defined as the proportion of patients achieving ≥50% reduction from baseline in the VAS score for POM at 72 hours)
- □ Responder rate 2 (defined as the proportion of patients able to resume training / normal physical activity by 168 hours)
- □ Clinical global assessment of efficacy as judged by investigator and patient at 48, 72 and 168 hours
- □ Overall dose of rescue medication needed (paracetamol)

Other:

Adhesive power of patch (5-point scale)

If there is significant use of rescue medication, a sensitivity analysis may be performed to assess impact on primary endpoint and responder rate.

Outcomes will be compared for all use of rescue medication and separately for use to treat blunt trauma. Day 1 and the day of the final visit will count as full days for this purpose. Use of rescue medication on days after study medication has been discontinued will not be counted.

9.7.2 Statistical hypothesis, model, and method of analysis For the primary variable an analysis-of-covariance (ANCOVA) with baseline as covariate and treatment, center and subgroup as factors will be carried out. An a priori ordered testing procedure controlling the multiple α -level of 5 % will be used in the analysis:

1) $H_{o:} \mu_E = \mu_P \text{ vs. } H_1: \mu_E \neq \mu_P.$

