- □ Time to meaningful relief will be censored (if appropriate) at the time of the final assessment of meaningful relief. If the patient discontinues for lack of efficacy before achieving meaningful relief, it will be censored at 24h.
- □ Time to perceptible relief will be censored (if appropriate) at 24h or the time of final assessment of spontaneous pain relief (if earlier). If the patient discontinues for lack of efficacy before achieving perceptible relief it will be censored at 24h.
- □ Time to resolution of blunt trauma will be censored (if appropriate) at the day of the final visit. If the patient discontinues for lack of efficacy, it will be censored at 7 days.
- □ Time to first use of rescue medication will be censored (if appropriate) at the last day for which diary records are available.

If a patient takes a disallowed analgesic medication and subsequently provides efficacy assessments, rules will be established on a case-by-case basis, taking into consideration whether

the disallowed analgesic medication was taken to treat pain in the injured area and the likely duration of effect of the medication. The rules will be documented before the study is unblinded.

Additional data handling rules will be specified in the Statistical Analysis Plan to cover issues not anticipated in the above stipulations.

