5.1.2 Secondary efficacy variables

- POM at injured site in mm measured using a 100 mm VAS at 12, 24, 48, 72, 96 and 168 hours after commencement of study treatment and will additionally presented by subgroups (table and Figure).
- AUC over time during first 12, 24, 48, 72, 96 and 168 hours for POM measured using a VAS; ordinate = POM score in mm, abscissa = time after treatment
- Pain-at-rest (PAR) at injured site in mm measured using a 100 mm VAS at 12, 24, 48 72, 96 and 168 hours.
- Reduction in VAS for POM from baseline:
 - Time to meaningful reduction (30%)
 - \circ Time to optimal reduction (50%)
 - Time to complete resolution of pain
- Responder rate 1 (defined as the proportion of patients achieving ≥50% reduction from baseline in the VAS score for POM at 72 hours)
- Responder rate 2 (defined as the proportion of patients able to resume training / normal physical activity by 168 hours)
- Clinical global assessment of efficacy as judged by investigator and patient at 48, 72 and 168 hours
- Overall dose of rescue medication needed (paracetamol).
- POM on VAS by indication at Visit 5.

Additional outcomes

- Adhesive power of patch (5-point scale)
- Mean adhesion by application site and/or net use.
- If there is significant use of rescue medication, a sensitivity analysis may be performed to assess impact on primary endpoint and responder rate.
- Outcomes will be compared for all use of rescue medication and separately for use to treat blunt trauma. Day 1 and the day of the final visit will count as full days for this purpose. Use of rescue medication on days after study medication has been discontinued will not be counted.
- POM on VAS difference at V4, V5, V6 compared to V1 (BL) (PID V4, PID V5, PID V6) PID V4, PID V5 and PID V6 will be compared between treatment groups using ANCOVA with terms in the model for treatment group, site [as fixed effects], and baseline POM assessment [as a covariate]. Least square mean for each treatment and the

CRMB	Trial Substance:	Esflurbiprofen Hydrogel Patch	Study No.: EudraCT No.:	TK-254R-0201 2020-005165-14
	Short Title:	Local symptomatic and short-term treatment of pain in acute strains, sprains or bruises of the extremities following blunt trauma		OKU SEIYAKU CO LTD.

corresponding difference between least square means with the p-value and 95 % confidence interval will be presented from the specified ANCOVA model.

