14.8 Missing data

- If assessments at any visit for Visits 2 (12 h) through Visit 6 (96 h) are missing, they will be imputed as the average of the preceding and the following assessments. Fractional values will be rounded down (including ordered categorical assessments). If assessment at Visit 7 is missing, the last observation will be carried forward.
- If a patient terminates prematurely,
 - all subsequent visits will be imputed by carrying the last non-missing observation forward.
 - for an adverse event suspected to be study-drug-related, then all subsequent visits will be imputed by carrying the baseline observation forward.
 - for lack of efficacy, all subsequent assessments will be imputed as the worst of all documented assessments.
 - for lack of efficacy or for an adverse event suspected to be study-drug-related and does not complete the global assessment of treatment satisfaction, it will be assigned the worst possible score.

CRMB	Trial Substance:	Esflurbiprofen Hydrogel Patch	Study No.: EudraCT No.:	TK-254R-0201 2020-005165-14
	Short Title:	Local symptomatic and short-term treatment of pain in acute strains, sprains or bruises of the extremities following blunt trauma	Sponsor: TEIKO	KU SEIYAKU CO LTD.

- If a patient discontinues for any other reason, missing global assessments at Visit
 7 will be imputed by LOCF from Visit 5 and missing assessments at Visit 5 will not be imputed.
- If a patient assesses efficacy at the site < 6 hours after using rescue medication, imputation will be discussed in the Blind Review Meeting, with consideration given to the frequency of this issue in the database and the elapsed time between rescue and assessment of efficacy.
- If a patient assesses spontaneous pain intensity and spontaneous pain relief at the time of rescue taken because of blunt trauma pain, any assessment conducted in the following 6 h will be replaced by the corresponding assessment done at the time of rescue.
- If a patient assesses spontaneous pain intensity and spontaneous pain relief at the time of rescue taken for reason other than blunt trauma pain, any assessment conducted in the following 6 h will be imputed as if the assessment were missed.
- If there are no assessments in the 12-24 h window, or the 24-48 h window,
 - if the patient has not prematurely terminated, a value from the last preceding assessment or assessment window will be carried forward.

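### The censoring rules name none of the three listed pain-on-movement time-to-event endpoints, and if *meaningful relief* means the 30% reduction, lack-of-efficacy withdrawals are all censored at 24 h

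*SAP*

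**What the plan says.** **Endpoints.** Protocol 9.7.1 and SAP 5.1.2 and 14.4.2 list three times to event under reduction in POM on the VAS: 30% (labelled meaningful), 50% (labelled optimal) and "Time to complete resolution of pain". POM is measured at 12, 24, 48, 72, 96 and 168 h. SAP 14.4.2 specifies a log-rank test stratified by center and calls all secondary tests exploratory.

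**Censoring.** SAP 14.9 repeats Protocol 9.7.3 and has four rules:

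| Variable named in the rule | General censoring | Lack-of-efficacy withdrawal |
|---|---|---|
| Meaningful relief | final assessment | 24 h |
| Perceptible relief | 24 h, or the final assessment if earlier | 24 h |
| Resolution of blunt trauma | day of final visit | 7 days |
| First rescue use | last diary day | none stated |

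The clause at issue reads "If the patient discontinues for lack of efficacy before achieving meaningful relief, it will be censored at 24 h" in the SAP and "If the patient discontinues for lack of efficacy before achieving meaningful relief, it will be censored at 24h" in the protocol.

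**Related text.** Protocol 7.5.1 defines injury resolution separately from pain: "Time to resolution is the time of last application of study medication because the soft tissue injury/contusion has resolved". For withdrawals, SAP 14.8 says: "for lack of efficacy, all subsequent assessments will be imputed as the worst of all documented assessments". For Visit 7, which includes POM, Protocol section 7 says: "Procedures for this visit are also to be completed if the patient terminates the study prematurely".

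**The concern.** A programmer given SAP 14.9 finds no rule under the name of any endpoint to be analysed. For the 30% endpoint the nearest rule treats two otherwise identical patients differently. Both are seen without relief up to 96 h. The one who moves away is censored at the final assessment; the one who leaves because the treatment failed is censored at 24 h. Only known failures are pulled back, so censoring depends on the outcome. Those left in the later risk sets are then too favourable a sample, and estimated relief rises in the arm with more late failures. If that arm is placebo, a real difference is partly masked; if it is the active arm, the drug is flattered.

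The category is not hypothetical: the protocol synopsis (Concomitant Treatment) withdraws certain patients as non-responders. How many there will be is not stated.

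**Working it through.** **1. Names side by side.** Endpoints named by a rule: 0 of 3. Rules naming a listed time-to-event endpoint: 0 of 4. Nothing corresponds to the 50% reduction. Resolution of blunt trauma is only a loose analogue of complete pain resolution. Perceptible relief is not a listed endpoint. Meaningful relief has one natural match, because the protocol synopsis (Assessments) attaches the word meaningful to the 30% reduction, but no text says they are the same.

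**2. Observation lost, if they are the same.** Time lost is the last visit seen unrelieved minus 24 h: 48 − 24 = 24 h, 72 − 24 = 48 h, 96 − 24 = 72 h. That is 1, 2 or 3 of the six visit risk sets. A patient leaving at 12 h is instead carried, unobserved, to 24 h.

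**3. Fit with the rest of the plan.** SAP 14.9 itself uses 7 days for a lack-of-efficacy withdrawal under injury resolution. Under SAP 14.8, a patient who never met the threshold has only documented values short of it, so the worst of them is also short. With imputed visits such a patient would stay event-free to 168 h, not 24 h. The SAP does not say whether event times use imputed visits.

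**4. Worked example (event counts assumed).** Take 100 placebo patients with cumulative 30% events of 3/8/20/35/50/70 at the six visits, of whom 10 without the event withdraw for lack of efficacy at 96 h.

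- 24 h rule: 92 are event-free after 24 h, so 92 − 10 = 82 are at risk at 48 h. Relieved by 72 h: 1 − 0.92 × (70/82) × (55/70) = 38.3%. By 96 h: 1 − 0.92 × (40/82) = 55.1%. By 168 h: 1 − 0.92 × (20/82) = 77.6%.
- Last POM (96 h): 35.0%, 50.0%, and 1 − 0.50 × (20/40) = 75.0%.

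With an active arm of 5/15/35/55/70/85, also assumed, the unstratified log-rank Z is:

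| Withdrawals at 96 h, active / placebo | 24 h rule | Last POM | Event-free to 168 h |
|---|---|---|---|
| 2 / 10 | 2.53 | 2.99 | 3.20 |
| 10 / 2 | 4.57 | 3.81 | 3.20 |

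**5. Smaller failure rates.** The only dropout figure is about 10% from all causes (SAP 6), so 10 per 100 is a ceiling. Assume exponential relief with mean 60 h and a proportion p of patients who are not failures. The 24 h rule gives S(24) = 1 − p(1 − e^(−24/60)) and S(96) = S(24) × e^(−72/60). Last-POM censoring at 96 h gives S(96) = 1 − p(1 − e^(−96/60)). For p = 0.90 these are 0.703 × 0.301 = 0.212 and 0.282, so 78.8% against 71.8% relieved, an overstatement of 7.0 points. For 5 and 3 failures per 100 it is 3.5 and 2.1 points. By 168 h the three values shrink to 2.1, 1.1 and 0.6. If withdrawal is at 48 h, the overstatement at 96 h is 1.5, 0.7 and 0.4 points.

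**6. Log-rank power (simulated).** Assumptions: 100 per arm, 3 centers, mean time to relief 45 h active and 60 h placebo, and withdrawals drawn from patients still unrelieved whose later course would match that of the others. Power without withdrawals is 49%.

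| Withdrawn, active / placebo | Spread over 12–96 h: 24 h rule vs last POM | All at 48–96 h: 24 h rule vs last POM |
|---|---|---|
| 1% / 3% | 47% vs 49% | 45% vs 48% |
| 2% / 5% | 46% vs 48% | 42% vs 48% |
| 2% / 10% | 37% vs 47% | 31% vs 47% |
| 5% / 5% | 47% vs 47% | 50% vs 48% |
| 10% / 2% | not tabulated | 71% vs 47% |

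Repeat runs moved individual entries by up to about 3 points, without changing the pattern. With identical arms and 5% withdrawal in each, the 24 h rule kept its level (0.050).

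**The case against.** The strongest reply is that the relief wording is leftover text. Meaningful relief stands beside perceptible relief and spontaneous pain relief, which no listed assessment collects, and both relief rules share a 24 h horizon that suits a short relief study. A reader might infer that the SAP definitely censors the 30% endpoint at 24 h; the documents do not support that, because they never link the terms. What stands is that, if the text is leftover, the 30% endpoint has no rule of its own, and the text still needs correcting.

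Second, a reader might infer that the 50% and complete-resolution endpoints have no handling at all. That is too strong. SAP 14.8 imputes all visits after premature termination without excepting time-to-event endpoints, so it may already govern them. For the same reason 14.8 and 14.9 are not a proven contradiction: they diverge only if both apply to the same event time, which is left open.

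Third, SAP 14.8 makes censoring a topic for the Blind Review Meeting. That is a genuine opportunity. However, SAP 14.9 sends to the minutes only rules for issues not anticipated, and the 24 h clause is already written.

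Fourth, last-POM censoring is not automatically right. The simulation in step 6 favours it by construction. Withdrawal as a non-responder, worst-value imputation and the 7-day rule all point towards failure through 168 h. This stands, and the fix leaves the choice open. Either option is better than discarding observed follow-up.

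**Conclusion.** The naming gap is certain. The censoring of known failures at 24 h is conditional on meaningful relief being the 30% POM reduction: the most natural reading, but an unstated one. On that reading the direction is fixed, since relief is overstated in the arm with more late failures, but which arm that would be is unknown.

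The size is also unknown. The documents give no lack-of-efficacy rate and no event rate or hazard for these endpoints. Under the stated assumptions the typical cost is about 2 to 3 points of power. Larger shifts need strongly unequal or late withdrawals, some with 10% lack-of-efficacy withdrawal in one arm, which equals the whole all-cause allowance. A reader might infer a threat to the trial's main conclusion; there is none. The primary ANCOVA at 72 h does not use these rules, and the endpoints are exploratory. The correction should still be made, because it costs almost nothing and no other text overrides the written clause.

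**What to change.** In SAP 14.9:

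- Replace the relief terms with the three POM endpoints, one rule each, over the full 168 h.
- Delete the 24 h lack-of-efficacy censoring and the perceptible-relief rule.
- Follow each patient without the event at least to the last valid observed POM assessment, at its actual time, and never censor earlier.
- Keep the rescue-window rules of 14.8 and the disallowed-analgesic rules of 14.9 when deciding which assessments can count as events. This matters for the termination visit, which Protocol 6.5.9 allows up to one week after study drug is stopped.
- State whether event times use imputed visits, so that 14.8 and 14.9 agree.
- For lack-of-efficacy withdrawals, choose before unblinding either last-POM censoring or not achieved through 168 h as the main analysis, and report the other as sensitivity.

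The cost is a few lines. SAP section 1 says the SAP is finalized after the blind review, so the change can be made before unblinding, and the POM data needed are already scheduled at early termination. Align Protocol 9.7.3 by amendment, or list the difference as a change from the protocol. Last-POM censoring still assumes that withdrawn patients resemble those who remain, which is why the second analysis is needed.
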